Trial Registration	This study will be registered on ClinicalTrials.gov by the Sponsor.
Test Article(s)	
Investigational Products:
 
 • senofilcon A contact lenses made with a novel manufacturing technology (Test). • senofilcon A contact lenses made with the current manufacturing technology (Control). 
Approved Products: None

Wear and Replacement Schedules	
Wear Schedule: daily wear
 
Replacement Schedule: daily disposable

Objectives	To evaluate the clinical performance of senofilcon A contact lenses made with a new manufacturing technology as compared to senofilcon A contact lenses made with the existing manufacturing technology.
Study Endpoints	
Co-primary endpoint(s):
 
 • Monocular distance visual performance after 1- and 2-weeks of lens wear • Average daily wear time (in hour) after 1- and 2-weeks of lens wear 
Secondary endpoint(s):
 
 • Overall comfort after 2-weeks of lens wear • Overall quality of vision after 2-week of lens wear 
Additional Endpoints:
 
 • Slit lamp findings • Subject reported ocular symptoms • Lens fitting characteristics • Lens wettability • Adverse events • Reasons for discontinuation • Lens damage • MRD/GSI items

Clinical Study Protocol
Johnson & Johnson Vision Care, Inc.

Study Design	
This study is a feasibility, multi-site, randomized, double-masked, 2-arm parallel group design, 2-week dispensing study with weekly visits. Subjects will wear bilaterally either the Test or Control lenses (randomly assigned) for 2-weeks in a daily disposable modality.
 
See the flow chart at the end of the synopsis table for the schematic of the study visits and procedures of main observations (Figure 1).

Sample Size	Approximately 115 eligible subjects will be enrolled and randomized into the study to ensure that approximately 100 subjects (~50 in the Test group and ~50 in the Control group) complete as cohort.
Study Duration	There will be a 6-week enrollment window. The study will last approximately 2 weeks per subject. Therefore, the entire study will last approximately 8 weeks per site.
Anticipated Study Population	Healthy male and female adults of any race and ethnicity who meet the eligibility criteria can participate. The study will target habitual wearers of daily disposable silicone hydrogel contact lenses.

Clinical Study Protocol

Johnson & Johnson Vision Care, Inc.

Eligibility Criteria - Inclusion	
Potential subjects must satisfy all of the following criteria to be enrolled in the study:
 
Inclusion Criteria following Screening The subject must:
 
1. Read, understand, and sign the STATEMENT OF INFORMED CONSENT and receive a fully executed copy of the form.2. Appear able and willing to adhere to the instructions set forth in this clinical protocol.3. Be between 18 and 39 (inclusive) years of age at the time of screening.4. By self-report, habitually wear spherical soft silicone hydrogel contact lenses in both eyes in a daily reusable or daily disposable wear modality (i.e. not extended wear modality). Habitual wear is defined as a minimum of 6 hours of wear per day, for a minimum of 5 days per week during the past 30 days.5. Possess a wearable pair of spectacles that provide correction for distance vision. 
Inclusion Criteria at Baseline Evaluation
 
6. The spherical equivalent of the subject's vertex-corrected distance refraction must be between -1.00 and -6.00 DS (inclusive) in each eye.7. The magnitude of the cylindrical component of the subject's vertex-corrected distance refraction must be between 0.00 and 1.00 DC (inclusive) in each eye.8. The best corrected, monocular, distance visual acuity must be 20/25 or better in each eye.
----------------------------------	---

Clinical Study Protocol

Johnson & Johnson Vision Care, Inc.

Eligibility Criteria – Exclusion	
Potential subjects who meet any of the following criteria will be excluded from participating in the study:
 
Exclusion Criteria following Screening The subject must not:
 
1. Be currently pregnant or lactating.2. Be currently using any ocular medications or have any ocular infection of any type.3. By self-report, have any ocular or systemic disease, allergies, infection, or use of medication that the investigator believes might contraindicate or interfere with contact lens wear, or otherwise compromise study endpoints, including infectious disease (e.g., hepatitis, tuberculosis), contagious immunosuppressive disease (e.g., Human Immunodeficiency Virus [HIV]), autoimmune disease (e.g. rheumatoid arthritis, Sjögren's syndrome), or history of serious mental illness or seizures. See section 9.1 for additional details regarding excluded systemic medications.4. Be currently wearing monovision or multifocal contact lenses.5. Be currently wearing lenses in an extended wear modality.6. Have participated in a contact lens or lens care product clinical trial within 7 days prior to study enrollment.7. Be an employee (e.g., Investigator, Coordinator, Technician) or immediate family member of an employee (including partner, child, parent, grandparent, grandchild or sibling of the employee or their spouse) of the clinical site. 
Exclusion Criteria at Baseline Evaluation The subject must not:
 
8. Have clinically significant (grade 3 or higher on the FDA grading scale) slit lamp findings (e.g., corneal edema, neovascularization or staining, tarsal abnormalities or bulbar injection) or other corneal or ocular disease or abnormalities that the investigator believes will contraindicate contact lens wear or may otherwise compromise study endpoints (including entropion, ectropion, chalazia, recurrent styes, glaucoma, history of recurrent corneal erosions, aphakia, moderate or above corneal distortion, herpetic keratitis). (Specify method of determination if needed).9. Have fluctuations in vision due to clinically significant dry eye or other ocular conditions.
----------------------------------	---

[figure not shown]
Clinical Study Protocol
Johnson & Johnson Vision Care, Inc.

	10. Have had or have planned (within the study period) any ocular or intraocular surgery (e.g., radial keratotomy, PRK, LASIK, iridotomy, retinal laser photocoagulation, etc.).
Disallowed Medications/Interventions	Disallowed medications include any medication that may interfere with contact lens wear (at the investigator's discretion). See section 9.1 for details regarding disallowed systemic medications.
Measurements and Procedures	Subjective assessments, physiological responses, fitting characteristics.
Microbiology or Other Laboratory Testing	None
Study Termination	The occurrence of an Unanticipated Adverse Device Effect (UADE) or Serious Adverse Event (SAE) for which a causal relationship to a test article cannot be ruled out, will result in stopping further dispensing investigational product. In the event of a UADE or SAE, the Sponsor Medical Monitor may unmask the treatment regimen of subject(s) and may discuss this with the Principal Investigator before any further subjects are enrolled.
Ancillary Supplies/ Study-Specific Materials	Sterile rewetting drops, ACUVUE Revitalens
Principal Investigator(s) and Study Institution(s)/Site(s)	A full list of Principal Investigators, clinical sites, and institutions is kept separately from the Study Protocol and is included in the study Trial Master File.

Clinical Study Protocol

Johnson & Johnson Vision Care, Inc.

Figure 1: Study Flowchart

Clinical Study Protocol

Johnson & Johnson Vision Care, Inc.

COMMONLY USED ABBREVIATIONS, ACRONYMS AND DEFINITIONS OF TERMS

ADE	Adverse Device Effect
ADHD	Attention Deficit Hyperactivity Disorder
AE	Adverse Event/Adverse Experience
BSCVA	Best Spectacle Corrected Visual Acuity
CFR	Code of Federal Regulations
CLUE	Contact Lens User Experience
COM	Clinical Operations Manager
CRA	Clinical Research Associate
CRF	Case Report Form
CRO	Contract Research Organization
████████	████████
D	Diopter
DMC	Data Monitoring Committee
eCRF	Electronic Case Report Form
EDC	Electronic Data Capture
ETDRS	Early Treatment Diabetic Retinopathy Study
FDA	Food and Drug Administration
GCP	Good Clinical Practice
HEV	High Energy Visible
HIPAA	Health Insurance Portability and Accountability Act
HIV	Human Immunodeficiency Virus
IB	Investigator's Brochure
ICH	The International Council for Harmonization
IEC	Independent Ethics Committee
IRB	Institutional Review Board
ISO	International Organization for Standardization
ITT	Intent-to-Treat
JJVC	Johnson & Johnson Vision Care, Inc.
LASIK	Laser-Assisted in Situ Keratomileusis
OD	Right Eye
OS	Left Eye
OU	Both Eyes
PIG	Patient Instruction Guide
PQC	Product Quality Complaint
PRK	Photorefractive Keratectomy
PRO	Patient Reported Outcome
QA	Quality Assurance
SAE	Serious Adverse Event/Serious Adverse Experience
SAS	Statistical Analysis System
SD	Standard Deviation
UADE	Unanticipated Adverse Device Effect
USADE	Unanticipated Serious Adverse Device Effect
UV	Ultraviolet
VA	Visual Acuity

Clinical Study Protocol

Johnson & Johnson Vision Care, Inc.

1. INTRODUCTION AND BACKGROUND

In the spirit of continuous improvement, JJVC has identified a new manufacturing technology for senofilcon A. The purpose of this clinical trial is to demonstrate whether this new manufacturing technology has any clinically relevant impact on the clinical performance of the contact lens.

1.1. Name and Descriptions of Investigational Products

This study will test two (2) senofilcon A design prototypes against each other. The Test lens will utilize a new manufacturing technology, while the Control lens will be made with the current manufacturing technology. Further details about the test articles are found in section 6 of this protocol.

1.2. Intended Use of Investigational Products

The intended use of the investigative products is for correcting refractive error. During the study, the study article will be worn bilaterally in daily wear, daily disposable modality for at least 6 hours per day, 5 days per week, for approximately 2 weeks. Only one study article will be worn by each subject.

1.3. Summary of Findings from Nonclinical Studies

All previous pre-clinical findings were deemed satisfactory prior to proceeding with clinical trials on humans. For the most comprehensive nonclinical information regarding senofilcon A refer to the latest version of the Investigator's Brochure (IB).

1.4. Summary of Known Risks and Benefits to Human Subjects

For the most comprehensive risk and benefit information regarding the senofilcon A prototypes, refer to the latest version of the Investigator's Brochure (IB).⁵

1.5. Relevant Literature References and Prior Clinical Data Relevant to Proposed Clinical Study

Neither the Test nor the Control are marketed products, and therefore no relevant literature exists. Refer to the Investigator Brochure for additional information of the study articles.

2. STUDY OBJECTIVES, ENDPOINTS AND HYPOTHESES

2.1. Objectives

Primary Objective(s)

To evaluate the clinical performance of senofilcon A contact lenses made with a new manufacturing technology as compared to senofilcon A contact lenses made with the existing manufacturing technology in the following areas:

- Monocular distance visual performance (in logMAR) after 2-weeks of wear
- Average daily wear time (in hours)

Clinical Study Protocol

Johnson & Johnson Vision Care, Inc.

Secondary Objective(s)

To evaluate the clinical performance of senofilcon A lenses made with a new manufacturing technology by comparison to senofilcon A lenses made with the manufacturing technology in the following areas:

- Overall comfort after 2-weeks of lens wear
- Overall quality of vision after 2-weeks of lens wear

2.2. Endpoints

Primary Endpoint(s)

Average daily wear time (in hours):

Average daily wear time will be calculated as the number of hours between subjects reported time of insertion and time of removal of the study lenses, on an average day, at 2-Week Follow up evaluation.

Visual performance

Visual performance will be calculated as monocular contact lens-corrected distance visual acuity using a logMAR visual acuity scale. This will be evaluated under both high luminance/low contrast conditions and low luminance/high contrast conditions at 4 meters from Early Treatment Diabetic Retinopathy Study (ETDRS) charts at the 2 Week Follow-up visit.

Secondary Endpoint(s)

CLUE Comfort and Vision Scores:

The co-primary endpoints for this study are subjective assessment of comfort and quality of vision after 14 ± 4 days of wearing the study lenses as a daily disposable.

Subjective assessment of comfort and vision will be performed using the Contact Lens User Experience™ (CLUE) questionnaire.⁵ CLUE is a validated patient reported outcomes (PRO) questionnaire used to assess patient experience attributes of soft contact lenses (comfort, vision, handling, and packaging) in a US contact-lens wearing population between 18 and 65 years of age. CLUE composite scores are derived using Item Response Theory (IRT) and follow a normal distribution with a population average score of 60 (SD 20), where higher scores indicate a more favorable/positive response. A 5-point increase in an average CLUE score translates into 10% shift in the distribution of scores for the population of soft disposable contact lens wearers.

Other Endpoint(s)

Slit Lamp Findings

Frequency and severity by eye of slit lamp findings (SLFs) including conjunctival injection, corneal edema, corneal neovascularization, corneal staining, tarsal abnormalities or any other complications. SLFs will be evaluated at fitting and post-fitting evaluation visits including unscheduled visits.

Clinical Study Protocol

Johnson & Johnson Vision Care, Inc.

Subject's Reported Ocular Symptoms

Frequency and severity by eye of subject's reported ocular symptoms and problems with the study lens at fitting and post-fitting evaluation visits including unscheduled visits.

Lens Fitting characteristics

Frequency by eye of mechanical lens fitting characteristics including lens centration and lens movement and overall lens fitting acceptability at fitting and 2-week follow-up evaluations.

Lens wettability:

Frequency and Grade by eye of lens wettability at 2-Week Follow-up evaluation.

MRD/GSI items:

The individual MRD/GSI items will be descriptively summarized

The following will be monitored and descriptively evaluated:

- Adverse events
- Reasons for discontinuation
- Lens damage

2.3. Hypotheses

This is a feasibility study and all the hypotheses are exploratory in nature.

Primary Hypotheses:

There are two co-primary hypotheses in this study. Both of them must be met to satisfy the primary objective of the study.

1. The Test lens will be non-inferior to the Control lens with respect to logMAR visual performance (using ETDRS visual acuity charts) at the 2-week follow-up visit. A non-inferiority margin of 0.05 logMAR will be used.
2. The Test lens will be non-inferior to the Control lens with respect to average daily wear time at 2-week follow-up visit. A non-inferiority margin of 1 hour will be used.

Secondary Hypotheses:

1. The Test lens will be non-inferior to the Control lens with respect to overall CLUE comfort score at the follow-up visit. A non-inferiority margin of -5 points will be used.
2. The Test lens will be non-inferior to the Control lens with respect to overall CLUE vision score at the follow-up visit. A non-inferiority margin of -5 points will be used.

All primary hypotheses of this study have to be met for study success.

Clinical Study Protocol

Johnson & Johnson Vision Care, Inc.

3. TARGETED STUDY POPULATION

3.1. General Characteristics

The population to be studied will be healthy male and female volunteers (at least 18 and not more than 39 years old) who are habitual wearers of daily disposable silicone hydrogel contact lenses, and have a spectacle astigmatism of ≤ 1.00 D in both eyes. Approximately 115 subjects will be enrolled to ensure approximately 100 subjects successfully complete the study.

3.2. Inclusion Criteria

Potential subjects must satisfy all of the following criteria to be enrolled in the study:

Inclusion Criteria following Screening

The subject must:

1. Read, understand, and sign the STATEMENT OF INFORMED CONSENT and receive a fully executed copy of the form.
2. Appear able and willing to adhere to the instructions set forth in this clinical protocol.
3. Be between 18 and 39 (inclusive) years of age at the time of screening.
4. By self-report, habitually wear spherical soft silicone hydrogel contact lenses in both eyes in a daily reusable or daily disposable wear modality (i.e. not extended wear modality). Habitual wear is defined as a minimum of 6 hours of wear per day, for a minimum of 5 days per week during the past 30 days.
5. Possess a wearable pair of spectacles that provide correction for distance vision.

Inclusion Criteria at Baseline Evaluation

6. The spherical equivalent of the subject's vertex-corrected distance refraction must be between -1.00 and -6.00 DS (inclusive) in each eye.
7. The magnitude of the cylindrical component of the subject's vertex-corrected distance refraction must be between 0.00 and 1.00 DC (inclusive) in each eye.
8. The best corrected, monocular, distance visual acuity must be 20/25 or better in each eye.

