5.3. Procedures for Maintaining and Breaking the Masking

Every attempt will be made to keep the clinical trial personnel involved in the study (e.g. data management, biostatistician and clinical operations) unaware of the identity of the assigned study lenses. The identity of the study lenses will be masked by having the blister packs labeled with the study number, lot number, sphere power, expiration date and the randomization codes. Only the unmasked biostatistician generating the lens fitting schedule will have access to the decode information that allows matching of the randomization codes to the test articles. The medical monitor will also have access to the decode information in case breaking the mask is necessary for the urgent medical treatment of a subject.

Under normal circumstances, the mask should not be broken until all subjects have completed the study and the database is finalized. Otherwise, the mask should be broken only if specific emergency treatment/course of action would be dictated by knowing the treatment status of the subject. In such cases, the investigator may, in an emergency, contact the medical monitor. In the event the mask is broken, the sponsor must be informed as soon as possible. The date, time, and reason for the unmasking must be documented in the subject record. The investigator is also advised not to reveal the study treatment assignment to the clinical site or sponsor personnel.

Subjects who have had their treatment assignment unmasked are expected to return for all remaining scheduled evaluations. Subjects who are discontinued will be replaced.

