6. STUDY INTERVENTION

6.1. Identity of Test Articles

The following contact lenses will be used in this study:

Clinical Study Protocol
Johnson & Johnson Vision Care, Inc.

Table 1: Test Articles

	Test	Control
Name	senofilcon A with novel manufacturing technology	senofilcon A with current manufacturing technology
Manufacturer	JJVC – 4GT	JJVC – 4GT
Lens Material	senofilcon A	senofilcon A
Nominal Base Curve @ 22°C	8.5	8.5
Nominal Diameter @ 22°C	14.3	14.3
Nominal Distance Powers (D)	-1.00 through -6.00 in 0.25 steps	-1.00 through -6.00 in 0.25 steps
Wear Schedule in Current Study	Daily wear	Daily wear
Replacement Frequency	Daily disposable	Daily disposable
Packaging Form (vial, blister, etc.)	Sterile blister pack	Sterile blister pack
New UV/HEV filter	Yes	Yes

Each subject will wear a maximum of 19 study lenses in each eye, and maximum of 38 study lenses for both eyes. With a total enrollment of 115 subjects approximately 4,370 lenses will be used in this study. As a parallel design, approximately 16,826 lenses for each study article, for a total of 33,652 will be over-labeled for this study.

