7. STUDY EVALUATIONS

7.1. Time and Event Schedule

Table 3: Time and Events

Visit Information	Visit 1 Screening, Baseline, Treatment 1	Visit 2 Treatment 1 Follow- up 1	Visit 3 Treatment 1 Follow-up 2	Final Evaluation
Time Point	Day 0	7 ± 2 days following Visit 1	7 ± 2 days following Visit 2	Normally immediately after Visit 3
Minimum lens wear time immediately prior to visit	Must wear habitual lenses	NA	NA	NA
Estimated Visit Duration	2.5 hours	1.5 hours	1.0 hours	0.5 hours
Study Informed Consent	X			
Demographics	X			
Medical History	X			
Eligibility Assessment	X			
Background CLUE Questionnaire	X			
Subject Reported Symptoms	X	X	X	
Distance Visual Acuity	X	X	X	
Spherocylindrical Refraction & VA	X			
Biomicroscopy & Eye Rinse	X	X	X	
Study Lenses Dispensed	X			
Lens Damage	X	X	X	
10 minutes settling	X			
Spherical Over- Refraction	X			
logMAR visual acuity (ETDRS charts)		X	X	

Clinical Study Protocol
Johnson & Johnson Vision Care, Inc.

Visit Information	Visit 1 Screening, Baseline, Treatment 1	Visit 2 Treatment 1 Follow- up 1	Visit 3 Treatment 1 Follow-up 2	Final Evaluation
Time Point	Day 0	7 ± 2 days following Visit 1	7 ± 2 days following Visit 2	Normally immediately after Visit 3
Minimum lens wear time immediately prior to visit	Must wear habitual lenses	NA	NA	NA
Estimated Visit Duration	2.5 hours	1.5 hours	1.0 hours	0.5 hours
Lens Fit Assessment	X	X	X	
Lens Surface Deposits & Lens Wettability Assessment	X	X	X	
Compliance		X	X	
Contact Lens Wear Time	X	X	X	
Follow-up CLUE Questionnaire		X	X	
Follow-up MRD/GSI Questionnaire		X	X	
Adverse Event Review		X	X	
Concomitant Medication Review	X	X	X	
Final Evaluation Form				X
Exit Refraction				X

Clinical Study Protocol
Johnson & Johnson Vision Care, Inc.

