7.2. Detailed Study Procedures

VISIT 1

The subjects must present to Visit 1 wearing their habitual contact lenses.

Visit 1: Screening		
Step	Procedure	Details
1.1	Statement of Informed Consent	
Each subject must read, understand, and sign the Statement of Informed Consent before being enrolled into the study. The Principal Investigator or his/her designee conducting the informed consent discussion must also sign the consent form.
 
Note: The subject must be provided a signed copy of this document.

1.2	Demographics	Record the subject's year of birth, age, gender, race and ethnicity.
1.3	Medical History and Concomitant Medications	Record the subject's medical history and concomitant medications.
1.4	Habitual Lenses	Record the subject's habitual lens type, parameters, wear modality and duration.
1.5	Contact lens wear times	Record the current wear time (WT) and comfortable wear time (CWT).
1.6	Eligibility after Screening	
All responses to Screening Inclusion Criteria questions must be answered "yes" and all responses to Exclusion Criteria must be answered "no" for the subject to be considered eligible.
 
If subject is deemed to be ineligible after screening, proceed to Final Evaluation and complete Subject Disposition. Refraction and Biomicroscopy forms do not need to be completed as part of Final Evaluation.

Visit 1: Baseline		
Step	Procedure	Details
1.7	Background PRO Questionnaire	Subject will complete questions regarding their experiences with their habitual lenses.
1.8	Subject-reported Ocular Symptoms	Subject Reported Ocular Symptoms and Problems

Clinical Study Protocol
Johnson & Johnson Vision Care, Inc.

Visit 1: Baseline		
Step	Procedure	Details
1.9	Distance visual acuity (VA)	Record the distance Snellen VA for OD, OS and OU with their habitual contact lenses in place. Subject must keep reading smaller lines until less than half the letters are correctly identified.
1.10	Remove habitual lenses	The subject's habitual lenses will be removed and stored in their own lens case. If they forgot to bring their lens case, one will be provided to them.
1.11	Subjective spherocylinder refraction and VA	Perform binocular subjective best spherocylinder refraction and record the best corrected Snellen VA for OD, OS and OU.

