1.12	Biomicroscopy	FDA Slit Lamp Classification Scale will be used to grade the findings and determine eligibility. If any of these slit lamp findings are Grade 3 or higher, the subject is discontinued from the visit as ineligible and may be rescheduled for another baseline visit for the randomization period. Limbal and Bulbar Conjunctival Hyperemia findings and detailed Corneal Staining Assessment will be recorded using a more detailed scale for internal purposes only. Conjunctival hyperemia should be assessed using the 0.5 increment grading scale.
1.13	Eye Rinse	The investigator or technician may rinse the subject's eyes thoroughly with sterile saline.
1.14	Iris Color	The investigator will record the subject's iris color based on the scale provided.

Clinical Study Protocol
Johnson & Johnson Vision Care, Inc.

Visit 1: Baseline		
Step	Procedure	Details
1.15	Eligibility after Baseline	
All responses to Inclusion Criteria questions must be answered “yes” and all responses to Exclusion Criteria questions must be answered “no” for the subject to be considered eligible.
 
One additional baseline examination is permitted to be performed if the subject does not meet the eligibility criteria at the initial baseline visit
 
If subject is deemed to be ineligible after baseline, proceed to Final Evaluation and complete all forms.

Visit 1: Treatment 1 Lens Fitting		
Step	Procedure	Details
1.16	Lens Selection	
Assign the study lens based on the randomization scheme. Subjects will only wear the Test lens on both eyes or the Control lens on both eyes.
 
Select the contact lens power based on vertex-corrected subjective best sphere refraction.

1.17	Lens Insertion	
The Investigator or the subject inserts the study lenses. Record the time of lens insertion.
 
Check for lens damage under the slit lamp before proceeding with lens settling.
 
Replace damaged lenses if applicable.
 
Ensure the subject is given a Patient Instruction Guide.

1.18	Lens Settling	Allow the study lenses to settle for a minimum of 5 minutes.
1.19	Subjective Best Sphere Over Refraction	Perform subjective best sphere refraction over the study lenses with a phoropter (adopt the maximum plus to maximum visual acuity (MPMVA) approach and record the best corrected distance visual acuity to the nearest letter (OD, OS, and OU).

Clinical Study Protocol
Johnson & Johnson Vision Care, Inc.

Visit 1: Treatment 1 Lens Fitting		
Step	Procedure	Details

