14.5. Primary Analysis

The co-primary endpoints for this study are the logMAR VA test at a 4-meter distance under either HLLC or LLHC and the average daily wear time at 2-week follow-up evaluated after 14 ± 4 days of lens wear. The primary analysis will be conducted on per-protocol populations.

Visual Performance

Monocular distance visual performance in logMAR scale at follow-up visits will be analyzed using a mixed model of repeated measurement (MMRM) for HLLC and LLHC respectively to compare between Test and Control lenses at 2-week follow-up. The model will include baseline logMAR, lens type, visit, and the interaction of lens type and visit as the fixed effect, and investigational site and patient as random effects. Baseline demographics such as age and gender have historically limited influence on objective visual performance; thus, in accordance with the principle of parsimony, will not be included in the model. The covariance of residual errors between two follow-up visits across periods for the same eye and subject across wearing periods will be modeled using an unstructured (UN) covariance structure.

The null and alternative hypotheses for non-inferiority of Test lens relative to Control are as follows:

$$H_0: \Delta > 0.05$$
$$H_A: \Delta \leq 0.05$$

Clinical Study Protocol

Johnson & Johnson Vision Care, Inc.

where Δ is the mean difference in logMAR between Test lens and Control lens (Test minus Control) at 2-week follow-up. Non-inferiority will be declared if the upper bound of the confidence interval of the mean difference between Test and Control is less than 0.05.

Average Daily Wearing Time

Average daily wear time will be analyzed using a similar MMRM model with fixed and random effects described in the primary analysis. Age and gender will also be included as fixed effects.

The null and alternative hypotheses for non-inferiority of Test lens relative to Control are as follows:

$$H_0: \Delta < -1$$
$$H_A: \Delta \geq -1$$

where Δ is the mean difference in average daily wearing time between Test lens and Control lens (Test minus Control) at 2-week follow-up. Non-inferiority will be declared if the lower bound of the confidence interval of the mean difference between Test and Control is greater than -1.

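### Sphere-only lenses leave up to 1.00 D of cylinder uncorrected in the co-primary acuity, and the model gives up some precision by not adjusting for it

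*Combined protocol and SAP*

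**What the plan says.** - **Eligibility (section 3.2, criterion 7).** The magnitude of the cylinder in the "vertex-corrected distance refraction must be between 0.00 and 1.00 DC (inclusive) in each eye".
- **Lenses.** Table 1 in section 6.1 gives one nominal distance power series, the same for both lenses (minus "1.00 through -6.00 in 0.25 steps"), with no cylinder or axis. Under section 5.3 the blister packs are "labeled with the study number, lot number, sphere power, expiration date and the randomization codes". Step 1.16 of section 7.2 reads: "Select the contact lens power based on vertex-corrected subjective best sphere refraction".
- **Measurement of cylinder.** Step 1.11 of section 7.2: "Perform binocular subjective best spherocylinder refraction and record the best corrected Snellen VA for OD, OS and OU". Section 5.1 requires baseline information to be collected before randomisation. It describes permuted blocks and mentions no stratification by refraction.
- **Acuity model (section 14.5).** "The model will include baseline logMAR, lens type, visit, and the interaction of lens type and visit as the fixed effect". Site and patient are random effects. The parsimony argument is about demographics: "Baseline demographics such as age and gender have historically limited influence on objective visual performance". Refraction is not discussed.
- **Acuity schedule (Table 3, section 7.1).** The row "logMAR visual acuity (ETDRS charts" is marked at Visits 2 and 3 only. The two acuities taken before lens assignment at Visit 1 are both Snellen: in habitual lenses (step 1.9) and with the spherocylinder correction (step 1.11).

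**The concern.** Uncorrected cylinder is an optical determinant of lens-corrected acuity that differs between eyes. It is known for every eligible eye before randomisation, because criterion 7 cannot be checked without it. The reason that section 14.5 gives for leaving out age and gender does not extend to it. Omitting a prognostic covariate of this kind leaves its contribution in the residual variance and widens the interval that is compared with a 0.05 logMAR margin. Both co-primary hypotheses must be met (section 2.3), so precision lost on acuity lowers the chance of meeting the primary objective. The study's data are also meant to inform the design of later trials (section 14.2), for which a residual SD adjusted for cylinder would be useful.

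**Working it through.** **Step 1: reproduce Table 7.** Inputs from section 14.2: 50 per arm, margin 0.05, two-sample t-test. With noncentral t on 98 degrees of freedom and noncentrality (0.05 − difference) / (SD × √(2/50)), a one-sided alpha of 0.05 returns all six printed values:

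| Difference | SD | Printed | One-sided 0.05 | One-sided 0.025 (the stated two-sided 0.05) |
|---|---|---|---|---|
| −0.01 | 0.08 | 0.981 | 0.981 | 0.960 |
| −0.01 | 0.09 | 0.952 | 0.952 | 0.910 |
| −0.01 | 0.10 | 0.909 | 0.909 | 0.844 |
| 0 | 0.08 | 0.928 | 0.928 | 0.872 |
| 0 | 0.09 | 0.867 | 0.867 | 0.785 |
| 0 | 0.10 | 0.799 | 0.799 | 0.697 |

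Section 14.2 states a two-sided 0.05, and section 14.5 gives no confidence level for acuity. Both bases are therefore carried forward.

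**Step 2: assumptions that the documents do not supply.**
- Slope: 0.05 to 0.15 logMAR per dioptre of uncorrected cylinder.
- Cylinder SD: 0.20 to 0.35 D. For scale, a continuous uniform spread over 0 to 1.00 D gives 1/√12 = 0.289, and equal numbers at each quarter-dioptre step give 0.354.
- Share of the cylinder signal already absorbed by the baseline acuity covariate: 0 to 90%.
- The Table 7 SD of 0.10 is taken as the SD before cylinder adjustment. As in Table 7, each subject counts as one value.

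**Step 3: effect of adjustment at SD 0.10 and zero difference.** R² = (slope × cylinder SD / 0.10)² × (1 − share absorbed). Residual SD = 0.10 × √(1 − R²). For example, slope 0.15, cylinder SD 0.35 and no absorption give R² = (0.0525/0.10)² = 0.276 and a residual SD of 0.0851.

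| Slope | Cylinder SD | Absorbed | R² | Residual SD | Power, one-sided 0.05 (from 0.799) | Power, one-sided 0.025 (from 0.697) |
|---|---|---|---|---|---|---|
| 0.05 | 0.20 | 90% | 0.1% | 0.09995 | 0.799 | 0.697 |
| 0.05 | 0.20 | 0 | 1.0% | 0.0995 | 0.802 | 0.701 |
| 0.10 | 0.289 | 50% | 4.2% | 0.0979 | 0.814 | 0.715 |
| 0.10 | 0.289 | 0 | 8.4% | 0.0957 | 0.829 | 0.734 |
| 0.15 | 0.35 | 90% | 2.8% | 0.0986 | 0.809 | 0.709 |
| 0.15 | 0.35 | 50% | 13.8% | 0.0929 | 0.848 | 0.760 |
| 0.15 | 0.35 | 0 | 27.6% | 0.0851 | 0.898 | 0.829 |

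**Step 4: is chance imbalance an additional harm?** The SD of the shift in the contrast from chance cylinder imbalance is slope × cylinder SD × √(2/50). This runs from 0.05 × 0.20 × 0.2 = 0.002 to 0.15 × 0.35 × 0.2 = 0.0105 logMAR. The unadjusted standard error is 0.10 × 0.2 = 0.020. At the top end (0.0105/0.020)² = 0.276, which is the R² in the last row above. The imbalance is thus the same variance component, already inside the planned interval.

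**Step 5: error rate without the term.** A simulation at a true difference of 0.05 used slope 0.10, cylinder equally likely at each quarter-dioptre step, total SD 0.10 and 20,000 runs. It rejected in 0.026 of runs against a nominal 0.025. The Monte Carlo standard error is √(0.025 × 0.975 / 20,000) = 0.0011, so there is no sign of inflation.

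**The case against.** The strongest objection is that the model already adjusts for baseline logMAR. If that is acuity in the habitual lenses (step 1.9), which criterion 4 requires to be spherical, it already carries much of the uncorrected-cylinder effect and the gain shrinks towards nothing. If it is the spherocylinder-corrected acuity (step 1.11), it carries none. The documents do not say which is used, and no ETDRS baseline is scheduled. The objection therefore limits the size of the gain but cannot be relied on to remove it. It also shows that the undefined covariate needs settling in the same edit.

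Other points also stand. The slope is wholly assumed. Table 7's SDs are scenarios not drawn from historical estimates, and are not described as raw or adjusted. The 20/30 continuance rule (steps 1.27 and 2.16) may keep out the eyes that lose most acuity. If a subject's two eyes differ in cylinder, the subject-level spread is smaller than the eye-level one. The hypotheses are declared exploratory, and a parsimonious model is legitimate.

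A reader might infer something stronger: that a chance difference in cylinder between arms biases the comparison or invalidates the non-inferiority test. The documents do not support that. Allocation is randomised 1:1; eligibility, the power range and the fitting rule are the same in both arms; and steps 4 and 5 of the working show the imbalance inside the interval and the error rate intact.

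**Conclusion.** The omission is real, but it is a missed precision gain and not an error in the test. Under the stated assumptions the power improvement runs from practically nil to about 10 points on the basis that reproduces Table 7 (0.799 to 0.898) and about 13 points at the stated two-sided 0.05 (0.697 to 0.829). The top of each range needs the steepest slope, the widest cylinder spread and no absorption by baseline acuity, all at once. The documents cannot narrow the range. The difference between the two alpha bases (0.799 − 0.697 = 0.102) is as large as the largest gain on the first basis and is a separate matter. The change is optional, but worth making because it is free.

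**What to change.** In section 14.5, prespecify the eye's baseline vertex-corrected cylinder magnitude from step 1.11 as a continuous fixed effect in both acuity models. In the same edit, name the Visit 1 acuity that supplies baseline logMAR and how a Snellen reading is converted to logMAR, or schedule an ETDRS baseline. The source should precede lens assignment; the acuities at steps 1.19 and 1.21 are taken through the assigned study lens and so are not baseline values.

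The cylinder term costs one sentence and one degree of freedom, with no new data, visits or subjects. Naming the baseline source costs another sentence; only a new ETDRS baseline would add a Visit 1 measurement. Both edits should be in place before unmasking, since adding the term afterwards would be post hoc.
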